10.3.3. Evaluation of Immunogenicity	50
10.3.4. Data Review during the Study.....	50
11. References	51

List of Tables

Table		Page
Table GPGE.4.1	Objectives and Endpoints	22
Table GPGE.7.1	Treatments Administered.....	32

List of Appendices

Appendix		Page
Appendix 1.	Abbreviations and Definitions	53
Appendix 2.	Clinical Laboratory Tests.....	58
Appendix 3.	Study Governance, Regulatory, and Ethical Considerations	59
Appendix 4.	Hepatic Monitoring Tests for Treatment-Emergent Abnormality	62
Appendix 5.	Blood Sampling Summary.....	63
Appendix 6.	Clinically Significant Adverse Effects	65
Appendix 7.	Pancreatic Monitoring	67
Appendix 8.	Contraceptive Methods.....	70

1. Protocol Synopsis

Title of Study:

Pharmacokinetics, Safety, and Tolerability of a Solution Formulation of LY3298176 in Healthy Subjects

Rationale:

A solution formulation of LY3298176 will be evaluated in upcoming Phase 3 studies. This solution formulation has a different composition from the lyophilized formulation for injection that was used in the Phase 1 study, and is being used in the ongoing Phase 2 studies.

Part A: Investigate the relative bioavailability of the solution formulation (test), compared to the lyophilized formulation (reference).

Part B: The pharmacokinetics (PK) of LY3298176 following administration via intravenous (IV) route will be investigated.

Part C: The safety, tolerability, and PK of LY3298176, following administration of up to a 10-mg dose via a titration regimen using a solution formulation.

Objective(s)/Endpoints:

Objectives	Endpoints
Part A: 
 Primary: To evaluate the PK of a single SC dose of LY3298176, administered as solution formulation (test) versus lyophilized formulation (reference) in healthy subjects Secondary: To investigate the safety and tolerability of LY3298176, administered to healthy subjects 	
 PK parameters, including AUC and C_{max}, AEs and injection site reactions
Part B: 
 Primary: To evaluate the PK of a single IV dose of LY3298176 in healthy subjects Secondary: To investigate the safety and tolerability of LY3298176, administered to healthy subjects via IV formulation 	
 PK parameters, including AUC AEs
Part C: 
 Primary: To evaluate the safety and tolerability of LY3298176, following multiple SC weekly doses of a solution formulation administered in healthy subjects. Secondary: To evaluate the PK of LY3298176, administered as a solution formulation 	
 AEs and injection site reactions PK parameters including AUC and C_{max}

Abbreviations: AEs = adverse events; AUC = area under the drug plasma concentration versus time curve; C_{max} = maximum observed concentration; IV = intravenous(ly); PK = pharmacokinetic(s); SC = subcutaneous(ly).

Summary of Study Design:

Study I8F-MC-GPGE is a single-center, Phase 1, Part A is a 2-period crossover study in healthy subjects to evaluate the relative bioavailability of a 5-mg solution formulation (test) administered subcutaneously (SC), compared to reconstituted lyophilized formulation (reference). Part B is a single-arm study in healthy subjects to evaluate the PK of 0.5-mg solution formulation of LY3298176 following IV administration. Part C will be conducted in healthy subjects evaluating safety, tolerability, and PK of doses up to 10 mg, administered via titration, using a solution formulation.

Treatment Arms and Planned Duration for an Individual:

Part A: Subjects will be screened over a 28 day period and will be randomized to 1 of 2 treatment sequences, according to the randomization table provided to the site. Each subject will receive a single SC injection of LY3298176 test formulation and a reference formulation in a 2 arm cross over design. Subjects will be admitted to the clinical research unit (CRU) on Day -1 and discharged on Day 8 of each period and will return to the CRU for Day 15, Day 21, and Day 35-37 procedures each period. Each dose will be separated by a minimum of 35 days. A follow-up (or early discontinuation) visit should occur 35-37 days after the last dose of the study drug.

Part B: Subjects will be screened over a 28-day period. Subjects will be admitted to the CRU on Day -1. On Day 1, following an overnight fast of at least 8 hours, subjects will receive a single IV dose of LY3298176 solution formulation, administered over 10 minutes. At a minimum, subjects will remain in the CRU for 8 days. Subjects may be required to remain in the CRU for longer than Day 8, at the investigator's discretion. Subjects will return to the CRU on Day 15, Day 35-37 and at greater than or equal to 70 days post-dose.

Part C: Subjects will be screened over a 28-day period. Subjects will be randomized to receive LY3298176 or placebo in doses of 5 mg (Day 1), 5 mg (Day 8), 7.5 mg (Day 15), and 10 mg (Day 22). Treatment will be administered via solution formulation at each of the doses. Subjects will be required to attend follow-up visits 35 days after the last dose and at least 70 days after the last dose.

Number of Subjects:

Up to 46 adult subjects will be enrolled to ensure that 34 complete the study:

- Up to 20 healthy subjects will be enrolled in order that at least 16 complete Part A
- Up to 10 healthy subjects will be enrolled in order that at least 6 complete Part B
- Up to 16 healthy subjects will be enrolled in order that at least 12 complete Part C

Statistical Analysis:**Safety:**

Continuous safety variables will be summarized using descriptive statistics. Categorical safety variables will be summarized using count and percentage. Vital signs data will be analyzed and summarized for each Part.

Pharmacokinetic:

Part A: To evaluate the PK for the 2 formulations, area under the drug plasma concentration versus time curve from time zero to infinity ($AUC_{[0-\infty]}$), and maximum drug plasma concentration (C_{max}) will be log transformed and analyzed using a linear mixed-effects model with treatment, period, and sequence as fixed effects, and subject as a random effect. The treatment ratio and the corresponding 90% confidence intervals [CIs] of the ratios will be reported.

Part B: Pharmacokinetic parameters will be summarized descriptively.

Part C: Pharmacokinetic parameters will be summarized descriptively.

2. Schedule of Activities

2.1. Study Schedule Protocol I8F-MC-GPGE, Part A

Procedure (Part A)	Screening	Periods 1 and 2												ET	Comments		
		Days	-28 to -2	-1	1	2	3	4	5	6	7	8	15	21	35 - 37 post dose period 1	35 - 37 post dose period 2	
Informed Consent	X																
Subject Admission to CRU			X														
Subject Discharge from CRU												X					Subjects may stay longer according to investigator discretion
Outpatient Visit	X												X	X	X	X	X
Investigational Product Administration					X												There is a minimum of 35 days washout period between doses for Period 1 and Period 2. Study drug will be administered SC after an overnight fast of at least 8 hours.
Medical History	X																
Height	X																
Weight	X	X												X	X	X	
Vital Signs (BP/PR/T) (supine)	X	X	P	24	48							X	X	X	X	X	Time points may be added for each study period, if warranted and agreed upon between Lilly and the investigator.

Procedure (Part A)	Screening	Periods 1 and 2														ET	Comments
Days	-28 to -2	-1	1	2	3	4	5	6	7	8	15	21	35 - 37 post dose period 1	35 - 37 post dose period 2		≥ 35 day washout between doses 1 and 2.	
Clinical Laboratory Tests	X	X								X			X	X	X	See Appendix 2 , Clinical Laboratory Tests, for details.	
Adverse Event		X	X	X	X	X	X	X	X	X	X	X	X	X	X		
Injection Site Reaction Assessment			P, 0, 6h, 12h	24h	48h											0-hour assessment should be performed within 5 minutes after subcutaneous injection. Additional assessments may be performed if deemed necessary by the investigator. Visual analog scale (VAS) score will be recorded	
PK Samples			P, 8h, 12h,	24h	48h	72h	96h	120h	144h	168h	336h	480h	X	X	X	Sampling times are relative to the start of dose administration (0 hr). Predose sample must be collected before dose administration. If a subject withdraws from the study prior to completion of scheduled PK sampling for a given period, every effort will be taken to draw an unscheduled blood sample for PK	

Procedure (Part A)	Screening	Periods 1 and 2														ET	Comments
Days	-28 to -2	-1	1	2	3	4	5	6	7	8	15	21	35 - 37 post dose period 1	35 - 37 post dose period 2		≥35 day washout between doses 1 and 2.	
																	assessment. This will not be required if a sample has already been taken within the previous 24 hours. For ET, a PK sample can be taken at any time during the visit timed close to the immunogenicity sample.
Pregnancy Test	X	X												X	X	X	All females only. Serum pregnancy test will be performed at screening. Urine pregnancy test will be performed at Day -1 for each period and at ET/Follow-up.
Physical Examination	X	X								X				X	X	X	After screening, medical assessment only performed to include medical review and targeted examination, as appropriate.
12-lead ECG	X	X								X				X	X	X	Single 12-lead ECG will be collected. ECGs must be recorded before collecting any blood samples. Subjects must be supine for

Procedure (Part A)	Screening	Periods 1 and 2														ET	Comments
Days	-28 to -2	-1	1	2	3	4	5	6	7	8	15	21	35 - 37 post dose period 1	35 - 37 post dose period 2			≥ 35 day washout between doses 1 and 2.
																	at least 5 minutes before ECG collection and remain supine but awake during ECG collection.
Genetic Sample			P														Single sample for pharmacogenetic analysis taken prior to dosing on Day 1 in Period 1 only.
Immunogenicity Samples			P										X	X	X	X	All samples for immunogenicity should be taken predose for period 1 and 2. Day ≥ 35 post dose 2 and at follow-up (Day ≥ 70). Time-matched PK sample should be collected at each time point.

Abbreviations: BP = blood pressure; CRU = clinical research unit; ECG = electrocardiogram; ET = early termination; h = hours; P = Predose;

PK = pharmacokinetics; PR = pulse rate; T = Temperature; VAS = visual analog scale.

Note: If multiple procedures take place at the same time point, the following order of the procedures should be used: ECGs, vital signs, and venipuncture.

2.2. Study Schedule Protocol I8F-MC-GPGE, Part B

Procedure (Part B)	Screening	Treatment											ET	Comments				
		Days	-28 to -2	-1	1	2	3	4	5	6	7	8	15	35 - 37				
Informed Consent	X																	
Subject Admission to CRU			X															
Subject Discharge from CRU												X			Subjects may stay longer according to investigator discretion			
Outpatient Visit	X												X	X	X	X		
Investigational Product Administration				X												Study drug will be administered after an overnight fast of at least 8 hours. Study drug will be administered over 10 min IV infusion		
Medical History	X																	
Height	X																	
Weight	X	X											X		X			
Vital Signs (BP/PR/T) (supine) (hours)	X	X	P	24h	48h							X		X		X	Time points may be added for each study period, if warranted and agreed upon between Lilly and the investigator.	
Clinical Laboratory Tests	X	X										X		X		X	Requires an 8 hour fast. See Appendix 2 , for details.	
Adverse Event		X	X	X	X	X	X	X	X	X	X	X	X	X	X			

Procedure (Part B)	Screening	Treatment													ET	Comments
Days	-28 to -2	-1	1	2	3	4	5	6	7	8	15	35 - 37	≥70 days			
PK Samples			P, 5 min, 10 min, 30 min 1h, 2h, 4h, 8h, 12h,	24 h, 36 h	48 h	72h	96h	120h	144h	168h	336 h	X	X	X	All sampling times are from start of infusion. (0 hr). Predose sample must be collected before dose administration. If a subject withdraws from the study prior to completion of scheduled PK sampling, every effort will be taken to draw an unscheduled blood sample for PK assessment. This will not be required if a sample has already been taken within the previous 24 hours. For ET, a PK sample can be taken at any time during the visit timed close to the immunogenicity sample.	
Pregnancy Test	X	X										X		X	All females only. Serum pregnancy test will be performed at screening. Urine pregnancy test will be performed at Day -1 and at ET/Follow-up.	
Physical Exam	X	X								X		X		X	After screening, medical assessment only performed to include medical review and targeted examination, as appropriate.	

Procedure (Part B)	Screening	Treatment												ET	Comments	
		Days	-28 to -2	-1	1	2	3	4	5	6	7	8	15	35 - 37	≥ 70 days	
12-lead ECG	X		X									X		X	X	Single 12-lead ECG will be collected. ECGs must be recorded before collecting any blood samples. Subjects must be supine for at least 5 minutes before ECG collection and remain supine but awake during ECG collection.
Genetic Sample				P												Single sample for pharmacogenetic analysis taken prior to dosing on Day 1.
Immunogenicity Samples				P									X	X	X	All samples for immunogenicity should be taken predose and follow up. Time-matched PK sample should be collected at each time point.

Abbreviations: BP = blood pressure; CRU = clinical research unit; ECG = electrocardiogram; ET = early termination; hr = hour(s); IV = intravenous(ly);

min = minute(s); P = Predose; PK = pharmacokinetic(s); PR = pulse rate; T= Temperature

Note: If multiple procedures take place at the same time point, the following order of the procedures should be used: ECG, vital signs, and venipuncture.

2.3. Study Schedule Protocol I8F-MC-GPGE Part C

Procedure (Part C)	Screen	Prestudy	Treatment																		ET/Follow-up
Days	-28 to -2	Before -2	-1	1	2	3	4	8 ^a	9	10	15 ^a	16	17	18	22 ^a	23	24	25	57	≥92	
Informed consent	X																				
Admission to CRU ^c			X					X			X				X						
Discharge from CRU						X				X			X				X				
Outpatient visits to CRU		X												X				X	X	X	
Distribution of glucose meters, test strips, diary, and GM training		X																			
Distribution of additional test strips, and diary.								X			X				X						
Administer study drug ^d				X				X			X				X						
Medical history	X																				

Procedure (Part C)	Screen	Prestudy	Treatment																		ET/Follow-up			
			Days	-28 to -2	Before -2		-1	1	2	3	4	8 ^a	9	10	15 ^a	16	17	18	22 ^a	23	24	25	57	
Height and weight ^e	X					X	P					P			P				P					X
Physical examination	X																							
Medical assessment ^f	X						P					P			P				P					X
Vital signs (BP/PR/T) ^g (hours)	X				X	P	X	X				P	X	X	P	X	X		P	X	X			X
ECG ^h	X					P												P						X
PK sampling (hours)						P , 8h 2 4 h	48 h	72h	P			P , 8h 24 h	48 h	72 h	P , 8h 24 h	48 h	72 h	P , 8h 24 h	48 h	72 h	X		X	
Clinical laboratory tests ⁱ	X					P												P						X
AEs/concomitant medications	X					X	X	X				X	X	X	X	X	X	X	X	X	X	X	X	X
Injection site reactions ^b						P , 0, 6h, 12h 2 4 h					P , 0, 6h , 12 h	24		P , 0, 6, 12	24		P , 0, 6, 12	24						

Procedure (Part C)	Screen	Prestudy	Treatment																	ET/Follow-up			
			Days	-28 to -2	Before -2		-1	1	2	3	4	8 ^a	9	10	15 ^a	16	17	18	22 ^a	23	24	25	57
Pharmacogenomic sample								X															
Immunogenicity								P							P							X	X

Abbreviations: AEs = adverse events; BP = blood pressure; CRU = clinical research unit; ECG = electrocardiogram; ET = early termination; GM = glucose monitoring; h = hours; P = Predose; PK = pharmacokinetic(s); PR = pulse rate; T= temperature.

^a Dosing day – subjects will be admitted to CRU the day prior to dosing.

^b Visual analog scale (VAS) score will be recorded

^c For each CRU admission, subjects must remain at the CRU at least 72 hours postdose or per medical judgment.

^d Study drug will be administered after an overnight fast of at least 8 hours.

^e Height measured at screening only. Weight will be measured twice in a consistent way, each predose. Scale needs to be calibrated (refer to Section 9.4.4).

^f Medical assessment will include a physical examination.

^g Vital signs(BP/PR/T) measurements: for each dose day: predose, 24 hr, 48 hr, and on or after Day 92 (follow-up/ET).

^h Single local safety ECGs will be measured at screening, predose Day 1, predose Day 22, predose Day 50 and follow-up/ET to take place on or after Day 92 (follow-up). Electrocardiograms must be recorded before collecting any blood for safety or PK samples and close to the time of the blood draw. Subjects must be supine for approximately 5 to 10 minutes before ECG collection and remain supine, but awake, during ECG collection.

ⁱ Clinical safety laboratory measures include chemistry, hematology, and urinalysis panels. Blood samples will be taken predose on all dosing days. Subjects will be required to fast for at least 8 hours before each blood sample is drawn.

3. Introduction

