Part C: 
 Primary: To evaluate the safety and tolerability of LY3298176, following multiple SC weekly doses of a solution formulation administered in healthy subjects. Secondary: To evaluate the PK of LY3298176, administered as a solution formulation. 	
 AEs and injection site reactions PK parameters including AUC and C_{max}

Abbreviations: AEs = adverse events; AUC = area under the drug plasma concentration versus time curve;

C_{max} = maximum observed concentration; IV = intravenous(ly); PK = pharmacokinetic(s); SC = subcutaneous(ly).

5. Study Design

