5.1. Overall Design

Study I8F-MC-GPGE (GPGE) is a single-center, Phase 1 study conducted in healthy subjects in 3 parts: Part A is a 2-period, 2-treatment, crossover design evaluating the relative bioavailability of 2 formulations of LY3298176; Part B, a single-arm design evaluating LY3298176 PK with IV administration; and Part C is a placebo-controlled, single-arm design evaluating the safety, tolerability, and PK of LY3298176 titrated, once-weekly for 4 weeks.

Part A: Part A is a randomized, 2-period, crossover study in healthy subjects to evaluate the relative bioavailability of 5 mg LY3298176, administered as a solution formulation (test), compared to a 5-mg dose administered SC as lyophilized formulation (reference). Treatment sequences and randomization are described in Section [7.2](#).

Each subject will provide informed consent for study participation, and will undergo a screening examination within 28 days prior to enrollment.

In each treatment period, subjects will be admitted to the clinical research unit (CRU) on Day -1. On the morning of Day 1, following an overnight fast of at least 8 hours, subjects will receive a single SC dose of LY3298176, administered according to their assigned treatment sequences. Blood samples will be collected predose and up to 480 hours postdose to measure LY3298176 concentrations. At a minimum, subjects will remain in the CRU for 8 days. The investigator (or qualified designee) will review all available inpatient safety data before discharging subjects from the CRU on the morning of Day 8, provided that the subjects are deemed medically fit. Subjects may be required to remain in the CRU longer than Day 8, at the investigator's discretion. The subjects will return to the CRU for follow-up visits on Days 21 and 35-37.

There will be a washout period of at least 35 days between doses in Periods 1 and 2. Based on the PK properties of LY3298176 (terminal half-life: approximately 5 days), a washout period of at least 35 days between doses in Periods 1 and 2 is considered adequate. Period 2 will repeat the same schedule as Period 1 with the Day 35 visit being the final study visit, which will include an antidrug antibody (ADA) sample at least 10 weeks after the first dose.

Part B: Part B is a single, 0.5-mg IV dose of LY3298176 solution formulation (or lyophilized formulation in absence of solution formulation) administered to healthy subjects.

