Subjects will receive a treatment regimen of either LY3298176 or placebo to be given as a SC dose on Days 1, 8, 15, and 22, after an overnight fast (at least 8 hours). Subjects randomized to LY3298176 will receive a 5-mg dose on Day 1 and Day 8, a 7.5-mg dose on Day 15, and a 10-mg dose on Day 22, administered via solution formulation (treatment specifics can be found in Section 7.1).

Each subject will be required to return to the CRU for outpatient visits and for a follow-up visit on Day ≥ 92 .

For all parts of this study pharmacokinetic sampling and safety assessments, including AE recording, medical assessments, clinical laboratory tests, vital signs measurement, and electrocardiograms (ECGs), will be performed according to the Schedule of Activities (Section 2).

Subjects will be admitted the day before dosing. The investigator (or qualified designee) will review all available inpatient safety data before discharging subjects from the CRU on Day 3 after the final study procedures, provided that the subjects are deemed medically fit. More information is outlined in the Schedule of Activities (Section 2.3).

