Appendix 5. Blood Sampling Summary

This table summarizes the approximate number of venipunctures and blood volumes for all blood sampling (screening, safety laboratories, and bioanalytical assays) during the study.

Protocol I8F-MC-GPGE Sampling Summary Part A

Type of Sample	Volume per Sample (mL)	Number of Samples per Subject	Total Volume (mL)
Screening tests ^a	17.0	1	17.0
Clinical laboratory tests ^a	6.5	6	39.0
Pharmacokinetics	3.0	29	87.0
Immunogenicity	6.0	6	36.0
Genetic	10.0	1	10.0
Loss by use of indwelling, intravenous cannula	1.0	3	3.0
Total:			192.0

^a Additional samples may be drawn, if needed, for safety purposes.

Protocol I8F-MC-GPGE Sampling Summary Part B

Type of Sample	Volume per Sample (mL)	Number of Samples per Subject	Total Volume (mL)
Screening tests ^a	17.0	1	17.0
Clinical laboratory tests ^a	6.5	4	26.0
Pharmacokinetics	3.0	23	69.0
Immunogenicity	6.0	4	24.0
Genetic	10.0	1	10.0
Loss by use of indwelling, intravenous cannula	1.0	9	9.0
Total:			155.0

^a Additional samples may be drawn, if needed, for safety purposes.

Protocol I8F-MC-GPGE Sampling Summary Part C

Type of Sample	Volume per Sample (mL)	Number of Samples per Subject	Total Volume (mL)
Screening tests ^a	17.0	1	17.0
Clinical laboratory tests ^a	6.5	3	19.5
Pharmacokinetics	3.0	21	63.0
Immunogenicity	6.0	4	24.0
Pharmacogenomic	10.0	1	10.0
Loss by use of indwelling, intravenous cannula	1.0	6	6.0
Total:			139.5

^a Additional samples may be drawn, if needed for safety, purposes.

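### Part C schedules no on-drug safety panel after the 10-mg dose: the last is predose Day 22 and the next is at Day ≥92 (minor, cheap to fix)

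*Protocol*

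**What the plan says.** Part C's primary objective (Protocol Table GPGE.4.1) is "To evaluate the safety and tolerability of LY3298176, following multiple SC weekly doses of a solution formulation administered in healthy subjects". Protocol 5.1 sets the 10-mg dose on Day 22, the last dosing day.

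The Part C schedule (Protocol 2.3) treats the safety assessments as follows:

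- **Laboratory tests.** The grid row shows screening, two predose marks and a follow-up mark. Footnote i says "Blood samples will be taken predose on all dosing days", which means Days 1, 8, 15 and 22. Appendix 5 counts three clinical laboratory samples after screening. Amylase and lipase follow the same schedule (Protocol 9.4.9).
- **ECGs.** Footnote h says "Single local safety ECGs will be measured at screening, predose Day 1, predose Day 22, predose Day 50 and follow-up/ET". The grid has no Day 50 visit, and no dose follows Day 22.
- **Vital signs.** Footnote g gives "for each dose day: predose, 24 hr, 48 hr", so these do cover the 10-mg dose.
- **Discharge.** Under Protocol 5.1 the investigator "will review all available inpatient safety data before discharging subjects from the CRU on Day 3". The grid has discharge on Day 24 and an outpatient visit on Day 25 for the last dose, but footnote c asks for a stay of at least 72 hours.

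SAP 9.4.3 lists laboratory data and flags out-of-range values without summarizing them. SAP 9.4.5 does not present ECGs.

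**The concern.** Safety is the primary purpose of Part C and 10 mg is its highest dose, yet every scheduled on-treatment panel is drawn before that dose is given. Appendix 7 says amylase and lipase are followed to look for effects on the exocrine pancreas. Its algorithm, and the hepatic retest rule in Protocol 9.4.5.1, start from a laboratory value. If no sample is scheduled while the 10-mg dose is on board, a silent rise that begins after it triggers neither. Unscheduled tests are usually prompted by symptoms, so they are weakest for a rise without symptoms. Part A, by comparison, draws a panel on Day 8 after each 5-mg dose.

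**Working it through.** **1. Reproduce Appendix 5, Part C.** Grid panels after screening are predose Day 1, predose Day 22 and Day ≥92, so 3 × 6.5 = 19.5 mL. The total is 17.0 + 19.5 + 63.0 + 24.0 + 10.0 + 6.0 = 139.5 mL, which matches. Footnote i would give 4 dosing days + follow-up = 5 panels, or 32.5 mL and a total of 152.5 mL, which does not match.

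**2. Does the reading of the grid matter?** The column positions are broken in the text available. The laboratory row has the same layout as the ECG row, for which footnote h names Day 22. A predose mark can fall only on a dosing day, and none is later than Day 22. Panels between the 10-mg dose and follow-up are therefore 0 under the grid and 0 under footnote i. Even if the final mark belonged to Day 57, that is 57 − 22 = 35 days after the dose, an interval that Protocol 5.1 treats as an adequate washout.

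**3. How far off drug is Day ≥92?** The half-life is from Protocol 5.1 ("terminal half-life: approximately 5 days"). 92 − 22 = 70 days, and 70 / 5 = 14 half-lives.

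**4. Modelled load.** This sums dose × 2^(−days since dose / half-life), in mg. Instantaneous absorption is an assumption.

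| Time | Calculation | Load (mg) |
|---|---|---|
| After 7.5 mg, Day 15 | 5 × 2^(−14/5) + 5 × 2^(−7/5) + 7.5 | 10.11 |
| Predose Day 22 | 5 × 2^(−21/5) + 5 × 2^(−14/5) + 7.5 × 2^(−7/5) | 3.83 |
| After 10 mg, Day 22 | 3.83 + 10 | 13.83 |
| Day 24 | 13.83 × 2^(−2/5) | 10.48 |
| Day 92 | 13.83 × 2^(−14) | 0.0008 |

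- Step in peak load from the third to the fourth dose: 13.83 / 10.11 = 1.37. The earlier peak is about 73% of the later one (72–74% for half-lives of 4–6 days and single-dose tmax from 0 to 3 days).
- Time for load to fall back to the predose Day 22 level: 5 × log2(13.83 / 3.83) = 9.3 days. For a 4-day half-life it is 4 × log2(12.80 / 2.80) = 8.8 days, and for 6 days it is 6 × log2(14.77 / 4.77) = 9.8 days. At a 5-day half-life, slower absorption (tmax up to 3 days) leaves it at 9.3–9.4 days.
- Part A's Day 8 panel, for comparison: 5 × 2^(−7/5) = 1.89 mg. Predose Day 22 in Part C is thus a real on-drug sample, at about twice that load.

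**5. Cost of one more panel.** 139.5 + 6.5 = 146.0 mL. If footnote i governs, 152.5 + 6.5 = 159.0 mL. Over 16 subjects, 16 × 6.5 = 104 mL.

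**The case against.** The case for leaving the schedule alone has substance.

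- **The dose is not unobserved.** The primary endpoint, adverse events and injection-site reactions, is collected after 10 mg. So are vital signs at 24 and 48 hours and self-monitored glucose. Extra enzymes (Protocol 9.4.9), extra ECGs (9.4.3) and extra safety samples (Appendix 5) are allowed. All of this stands. A reader might infer that no laboratory result follows the 10-mg dose, but the Day ≥92 and early-termination panels do. What is missing is an on-drug panel for completers.
- **The discharge review has a panel.** A reader might infer that this review has no laboratory data. Subjects are admitted the day before dosing, so the predose Day 22 panel belongs to the same stay. Only a postdose result is absent.
- **Load is not detection.** The Day 24 load is 10.48 / 3.83 = 2.7 times the predose Day 22 load, which invites a claim that much is missed. That ratio sets a near-peak time against a trough. The step in peak is about 1.4-fold, and a rise after 7.5 mg that lasted a week would show at predose Day 22. The documents do not say when enzyme changes appear, so neither the ratio nor the 9 days measures missed detection.
- **Prior data and yield.** Protocol 3.3 reports no clinically significant concern with weekly doses titrated to 10 mg in Study GPGA, and 3.2 records 15 mg in patients. With 12–16 subjects at 3:1, 9–12 receive active drug. For an assumed 5% incidence, one panel would show at least one case with probability 1 − 0.95^9 = 37% to 1 − 0.95^12 = 46%.

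These points limit the severity. They do not supply the missing panel.

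**Conclusion.** The gap is real and minor. Completers have no scheduled on-drug safety panel after the fourth and highest dose, whether the grid or footnote i governs. This rests on counting visits and needs no model; placing the grid's second predose mark on Day 22 is an inference. The load figures depend on the 5-day half-life (4–6 days tried) and on assumed absorption, and serve only to show that Day ≥92 is long after washout and that Day 24 is well on drug.

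The benefit of closing the gap lies in clinical monitoring and in the listings. No summary or inference changes, because the SAP only lists laboratory data. The Day 50 ECG, the 5-versus-3 panel count and the 72-hour stay against Day 24 discharge are editorial conflicts. A reader might take them as the cause of the gap, but footnote i applied in full still ends at predose Day 22.

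**What to change.** Add one fasting safety panel, including lipase, amylase and ALT, at the existing 48-hour PK draw on Day 24, before discharge from the unit. If it is meant to inform the discharge review, say that results must be available first; the documents give no turnaround time. The 72-hour draw on Day 25 is a fallback. It still gives an on-drug panel, but under the grid it comes after discharge and cannot inform that review.

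The change is schedule wording in an amendment, with no new visit and no extra venipuncture. Appendix 5 goes from 3 to 4 panels and from 139.5 to 146.0 mL. The downsides are 6.5 mL of blood per subject, an overnight fast, and possible work-up of an incidental enzyme rise under Appendix 7.

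As an editorial correction only, make footnote c (72-hour stay), footnote h (drop the Day 50 ECG or assign it to a real visit), footnote i (all dosing days), the grid and Appendix 5 agree.
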